10.1.4 FUTURE USE OF STORED SPECIMENS AND DATA

The cortisol levels will not be assayed until after the study is complete given the relatively short nature of the study. However, the specimens will not be retained beyond their use in the study. As such, there is no additional information provided to the participants about these samples in the informed consent beyond the fact that we will request and analyze them.

The DSMB will operate under the rules of an approved charter that will be reviewed at the first DSMB meeting and approved by the members prior to the start of the trial. The DSMB will provide its input to appropriate individuals at the NIA.

Data Safety and Monitoring Board – Meeting timelines

The initial DSMB meeting will begin prior to the 400-participant pilot scheduled for May of 2024. Following that meeting, the NIH default meeting schedule for a DSMB is every 6 months. However, this study recruits participants very rapidly and those participants are then only enrolled for 3 (active) months and a one-month follow-up. After this period, there is a pause on study activities where no further participants are enrolled for eight months. Then, the process resumes. Given this timeline, the default meeting timelines every six months are ill-suited for this study.

Here instead we will plan to meet with the DSMB after sufficient data has been collected within a wave to ensure issues are identified as they arise. This allows for more timely feedback from the DSMB and, also, reduces the number of meetings with the DSMB in which no new information is available to be presented. In other words, we will arrange for the DSMB to meet once per year roughly 4 periods into the study (typically in June) during the active phase and will present information on the safety and efficacy of each arm at that time.

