Randomization will be done using statistical software for the treatment assignments and a process of drawing sealed envelopes for the period-by-period realizations in the Unpredictable Instability arm (to increase trust in the randomization process). The Control, Stable, Predictable Volatility arms will each have 400 participants. The Unpredictable Instability arm is overweighted with 1,067 participants, as the analysis of this arm will be disaggregated depending on the draws realized by each participant. The participant will learn of their study arm assignment after consent and the baseline survey, but prior to the beginning of the first 2-week period. The PIs and associated staff under their direction will generate the randomization code and output, with the exception of the period-by-period draws for the Unpredictable Instability participants which will occur in the field.

Unpredictable Instability participants will realize their draw for the next period in the five days between the time when the work for the prior period is completed and the work for the next period begins. This randomization is assured to be truly random via the following procedure:

- The field officer arrives at the participant's house with two sealed envelopes. One contains a "high" draw and the other a "low" draw for the period, as indicated by a work calendar. Both have the participant's ID number on the outside of the reverse (sealed) side of the envelope.
- The participant selects and opens one envelope
- The field officer photographs the calendar from the open envelope in the same frame as the sealed envelope with the same participant ID. This ensures that we can verify which envelope was opened first, and hence the draw of the participant for that period.
- The participant then opens the second envelope to verify that it held the other type of calendar/draw.

While we do not anticipate having randomization errors, should they occur, we will drop those participants from the study.

Each participant will be enrolled for 6 2-week periods. In addition, they will respond to an eligibility survey roughly 2-4 weeks prior to enrollment and complete a follow-up survey 1 month following the end of the active study period.

All participants will be enrolled from a single site surrounding Tamale, Ghana.

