5.5 STRATEGIES FOR RECRUITMENT AND RETENTION

We expect to screen roughly 10,000 households to reach our enrollment target of 2,267 participants. Households to be screened will be determined by a random sampling procedure within the targeted villages until the target number of households is reached. The target number of households per village will be a function of the village size, to ensure a relatively sparse randomization. These interviews will be conducted in person as in-person data collection will result in more accurate screening data and avoid any concerns around unreliable cell service and limited literacy. All of these households will be located in the vicinity of Tamale, Ghana. Local enumerators who are fluent in the local dialects and familiar with these areas will be enlisted to undertake this screening. Enumerators will not work after dark for their safety in traveling. To ensure participant safety, the interview will take place in a location of the participant's choice near or in their home and the study team will conduct back-checks and flag any discrepancies from protocols for review with a supervisor.

The screening will produce a household roster to identity potentially eligible individuals within the household. Consistent with the inclusion and exclusion criteria of the study, these individuals will be non-pregnant women between 18-65 years old living in (relatively) small households.

This process will result in roughly 2,267 African women between the ages of 18-65 being enrolled into the study (see inclusion/exclusion criteria for justifications for age restrictions).

The household screening survey used to determine eligibility will be conducted over the course of approximately 4-5 weeks in the spring of 2025. We will then enroll all participants in the study in 2-4 weeks in late March to early May of 2025. The pilot study will be conducted in the late spring/early summer of 2024.

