7.1 DISCONTINUATION OF STUDY INTERVENTION/EXPERIMENTAL MANIPULATION

No interim analysis is planned because the study is minimal risk (i.e. participants are always able to opt out of the work offered, neither the work nor the surveys are riskier than everyday activities). Given this, there are no study stopping rules for the study as a whole. Similarly, there are no criteria for individual discontinuation, should the individual wish to continue.

However, we do anticipate that individuals may need to discontinue participation at times and may wish to restart later. For example, the study takes place in an area with high disease burden. Hence, an individual who falls ill with a fever may wish to stop participation for a few weeks to recover and then rejoin.

We do not anticipate any SAE, AE, or UP in the administration of the study given that the work (sewing bags) is low-risk and the surveys are no more than minimal risk. Further, because the income generated by the study can be very valuable, both in material and psychological terms, we do not plan to involuntarily remove anyone from the study as the result of an adverse event unless they would like to discontinue. Should an individual wish to discontinue, we would collect any remaining sewing, make the corresponding payments, and thank the participant for their participation. If the individual wishes to restart at a later date (while the study was still ongoing),

they would be allowed to do so and would simply rejoin as soon as logistically possible (typically within one week).

Should an unanticipated AEs or SEA arise that was determined to be study related (to be determined by the site investigator and the PI following the procedures in the data safety and monitoring plan), this would be reported to the relevant IRB within 48 hours and to the DSMB members at the next DSMB meeting. For AEs and SEAs related to health, participants will be referred to the closest government health post or hospital, depending on the severity of the event. The costs of transportation for AEs and SEAs considered related or potentially related to study participation will be covered by the study.

If they so wish, their participation in the study would be halted until they felt able and willing to rejoin.

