8.3.6 SERIOUS ADVERSE EVENT REPORTING

A summary of all SAEs will be reported to the NIA Program Officer quarterly during all times when participants are enrolled, unless otherwise requested. Additionally, SAEs will be reported to the DSMB at all meetings which follow active periods of participant enrollment.

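### No scheduled DSMB meeting sees the last third of the pilot's work programme, its endline or its follow-up before all 2,267 main-trial women are enrolled

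*Combined protocol and SAP*

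**What the plan says.** Section 10.1.6 sets the calendar. "The initial DSMB meeting will begin prior to the 400-participant pilot scheduled for May of 2024". It then sets aside the six-monthly default because "those participants are then only enrolled for 3 (active) months and a one-month follow-up", after which "there is a pause on study activities where no further participants are enrolled for eight months". In its place, "we will arrange for the DSMB to meet once per year roughly 4 periods into the study (typically in June) during the active phase", and the board is to see safety and efficacy for each arm at that meeting. The stated aims are to catch issues as they arise and to avoid meetings with nothing new to present.

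Three other places bear on this:

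- Section 5.5, on the main trial: "We will then enroll all participants in the study in 2-4 weeks in late March to early May of 2025".
- Section 7.1, on unanticipated study-related events: to the IRB within 48 hours, but "to the DSMB members at the next DSMB meeting".
- Section 8.3.6: "SAEs will be reported to the DSMB at all meetings which follow active periods of participant enrollment", with a quarterly SAE summary to the NIA Program Officer while participants are enrolled.

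**The concern.** The pilot is the only part of the study that finishes before the step up from 400 to 2,267 women. A single meeting about two thirds of the way through the work programme cannot see how that programme ends, and the next scheduled meeting comes after the main trial has enrolled everyone.

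What is missed is not just more of the same data. The schedule of activities (Section 1.3) places the full psychological battery and the repeat blood pressure and weight measurements at the endline. At period 4 the board would have only short phone measures, and no blood pressure after baseline. It would also have nothing from the weeks after paid work stops.

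By-arm board review carries extra weight here for two reasons. Section 8.2 does not collect adverse events systematically and relies on a hotline and an open-ended survey question. Section 7.1 sets no stopping rules.

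**Working it through.** **Inputs.** Six two-week periods (Section 4.1: "Each participant will be enrolled for 6 2-week periods"). Follow-up 4 weeks after the programme. Pilot of 400 (Section 10.1.6), enrolled in late April and May 2024 (Sections 1.3 and 8.1). Main enrolment late March to early May 2025 (Section 5.5). Meetings about 4 periods in, typically June (Section 10.1.6).

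**The plan's own cycle.** 3 active months + 1 month follow-up + 8 months pause = 12 months. This agrees with one meeting a year. Arm sizes: 3 × 400 + 1,067 = 2,267, as stated.

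**Share of a wave passed at the meeting.** 4 periods × 2 weeks = 8 weeks.

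- Of the work programme: 8/12 = 67% passed, 4/12 = 33% (periods 5 and 6) still to come.
- Of the whole observation time: 8/(12 + 4) = 8/16 = 50%.
- With the day counts in Section 1.3 (work to day 74, follow-up to day 102): 56/74 = 76% and 56/102 = 55%. The conclusion is the same.
- In participant-weeks for the pilot, assuming everyone starts together and none is lost: 400 × 8 = 3,200 of 400 × 16 = 6,400 are unseen.

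**Calendar.** The documents give windows, not exact dates. I assumed pilot starts from 22 April to 31 May 2024 and main starts from 24 March to 10 May 2025. End of period 4 = start + 56 days; end of work = start + 84 days; follow-up = start + 112 days.

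| Wave | End of period 4 | End of work | Follow-up |
|---|---|---|---|
| Pilot | 17 June to 26 July 2024 | 15 July to 23 August 2024 | 12 August to 20 September 2024 |
| Main | 19 May to 5 July 2025 | 16 June to 2 August 2025 | 14 July to 30 August 2025 |

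If main enrolment closes on 10 May 2025, a meeting between 1 and 30 June 2025 comes 22 to 51 days later, or 3.1 to 7.3 weeks. Everyone is already enrolled.

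The 8-of-16 figure takes the roughly-4-periods description at face value. If the pilot meeting were fixed at mid-June 2024, women would be between 1.1 and 3.9 periods in, and the board would have seen less.

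**Delay for a late-pilot event under Section 7.1.** An event just after a June 2024 meeting waits about 12 months for the June 2025 meeting. An event at the last follow-up (20 September 2024) waits at least until 1 June 2025: 254 days, a little over 8 months.

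**Room for an extra review.** From the latest pilot follow-up (20 September 2024) to the earliest main start (24 March 2025) is 185 days, about 26 weeks. A six-monthly meeting counted from the pre-pilot one would have fallen around October or November 2024, with the complete pilot in hand. The reason given for dropping the default, that there would be nothing new to present, does not hold for that meeting.

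**The case against.** The schedule is a reasoned choice: meeting while a wave is active lets the board act on it, and Section 7.1 classes the study as minimal risk. That rationale supports the mid-wave meeting. It does not argue against a second look at the completed pilot.

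A reader might go further in several ways that the documents do not support.

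- *That half of the pilot's intervention goes unseen.* It is the last third of the work weeks. One half is reached only by counting the four weeks after work ends, which hold no study work and one short phone survey.
- *That late-pilot harm would reach nobody, or that the board clears the main trial by default.* Related adverse events go to the IRB at once (Section 8.3.5) or within 48 hours (Section 7.1). SAE summaries go to the NIA quarterly (Section 8.3.6). Deaths and unanticipated related SAEs are expedited to the NIA (Section 8.4.2). High PHQ scores and suicidal ideation trigger counselling contact (Section 8.2). No text says the board approves the main trial by silence. The charter is not included, and the text just before the meeting timeline was not available to me, so ad hoc meetings may be allowed.
- *That Section 8.3.6 contradicts Section 10.1.6.* Its wording can mean after the short enrolment window, which a period-4 meeting satisfies, or after the active phase, which it does not. It is ambiguous, not a proven conflict.
- *That the end of paid work is an established psychological risk.* The plan does not say so, and Section 2.3.1 foresees no long-term risks. It is only a reasonable thing to want to look at.
- *That a board review after main-trial follow-up would cure the problem.* By then all participation is over and the board cannot alter the trial. At most it is a close-out report.

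What stands from the other side is that individual serious events have other routes. Those routes carry single events or summaries, whereas Section 10.1.6 gives the by-arm view to the board. An ad hoc power also helps little if the board learns of an event only at its next meeting.

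**Conclusion.** The point holds for scheduled DSMB review. On the visible calendar, no meeting sees pilot periods 5 and 6, the endline or the one-month follow-up (4 of 12 work weeks, 8 of 16 weeks in all) before the 2,267 are enrolled. Under Section 7.1 a study-related event late in the pilot could reach the board roughly 8 to 12 months after it occurs. This is a limited gap with an inexpensive remedy, not a failure of oversight as a whole.

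The conclusion rests on meetings being held about when Section 10.1.6 says, on starts within the stated windows, and on no end-of-pilot review being laid down in the charter or the monitoring plan. The exact dates are assumptions. The order of events does not depend on them, because every pilot follow-up ends by about late September 2024 and main enrolment closes before June 2025 under any dates in the windows.

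**What to change.** 1. **Section 10.1.6:** keep the mid-wave meeting. Add one DSMB review, in writing or by teleconference, during the eight-month pause: after the pilot's one-month follow-up and before the first main-trial enrolment. It should cover complete pilot AEs and SAEs, suicidal-ideation reports and counselling referrals, by arm.
2. **Sections 7.1 and 8.3.6:** notify the DSMB chair of study-related SAEs on the same 48-hour clock as the IRB, in place of waiting for the next meeting.
3. **Section 8.3.6:** state which meetings are meant by those that follow active enrolment periods, and reconcile this with the Section 10.1.6 calendar.
4. If the charter already provides for ad hoc meetings or an end-of-pilot report, cite it in Section 10.1.6.

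The cost is a short report, a little board time, about a paragraph of text and one more sign-off before the main trial starts. With about 26 weeks between the last pilot follow-up and the earliest main enrolment on the assumed dates, the review need not delay the start.

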10.1.7 CLINICAL MONITORING

N/A

10.1.8 QUALITY ASSURANCE AND QUALITY CONTROL

Quality control (QC) procedures will be implemented as follows:

Informed consent – Study staff will review both the documentation of the consenting process as well as a percentage of the completed consent documents. This review will evaluate compliance with GCP, accuracy, and completeness. Feedback will be provided to the study team to ensure proper consenting procedures are followed.

Survey fidelity – Electronic surveying will be used to improve survey fidelity. For example, this method allow us to validate data in real-time via checks on appropriate values and ranges, provide consistent administration of mental health measures through pre-recorded audio, and monitor surveyor time and location to identify outliers and allow supervisors to determine the cause of such outliers.

Intervention Fidelity – Consistent delivery of the study interventions will be monitored throughout the intervention phase of the study. Procedures for ensuring fidelity of intervention delivery are described in Section 6.2.1, Interventionist Training and Tracking.

Protocol Deviations – The study team will review protocol deviations on an ongoing basis and will implement corrective actions when the quantity or nature of deviations are deemed to be at a level of concern.

Should independent monitoring become necessary, the PI will provide direct access to all trial related sites, source data/documents, and reports for the purpose of monitoring and auditing by the sponsor/funding agency, and inspection by local and regulatory authorities.

10.1.9 DATA HANDLING AND RECORD KEEPING

10.1.9.1 DATA COLLECTION AND MANAGEMENT RESPONSIBILITIES

Data collection will be the responsibility of the clinical trial staff at the site under the supervision of the site investigator. The investigator will be responsible for ensuring the accuracy, completeness, legibility, and timeliness of the data reported.

High Frequency Checks (HFCs), Back Checks (BCs), and Spot Checks will be designed by IPA project staff to monitor and measure quality of the data collected by enumerators. These checks will help detect survey related issues such as questionnaire programming errors, data fabrication, surveyor errors and poorly understood questions among others.

Daily HFCs will be conducted on incoming data to flag potential survey and response errors for prompt correction and reconciliation. Checks for survey coding inconsistencies, missing data, outliers, too many similar responses, duplicates in respondent IDs, survey progress and surveyor performances will be implemented on incoming data using Stata commands and SurveyCTO built in features.

During data collection in the first week, all enumerators will be accompanied by their team leaders or supervisors to provide the necessary support to ensure the collection of high-quality data. Spotchecks by the team leader or field supervisor will also be done. In the case of accompaniment, a team leader or field supervisor will visit enumerators while an interview is ongoing to monitor the line of questioning, understanding of questions, observance of survey protocols and the overall conduct of surveyors in an uninterrupted manner and feedbacks provided to enumerators for improvement. For spot-checks, team leaders or field supervisors will pay an unannounced visit to enumerators to ascertain that the survey is ongoing, at the right place and at the right time.

In addition, back-checks (BCs) will be conducted on already interviewed respondents using some selected questions from the questionnaire. BCs will be administered by an "auditor", who will be different to the surveyor that administered the original survey to the specific respondent. This will help to check the consistency of the responses by participants. The standard practice at IPA is that at least 10% of all surveys for all surveyors must be back checked in the first week of survey launch. The responses from the back checks are compared to the original questionnaire responses to see if there are any discrepancies. The aim is to check for the accuracy of responses, the robustness of the instrument, the performance of surveyors and the potential falsification of data by them. In the case where discrepancies are detected, further probing will be conducted to know the sources of those discrepancies and actions taken to reconcile them.

Data security measures are described in Section 10.1.3.

10.1.9.2 STUDY RECORDS RETENTION

The NIH requires that the records be retained for three years following the completion of the study. This study will comply with that policy. After that time identifiers will be destroyed and only de-identified data will be retained and made available.

10.1.10 PROTOCOL DEVIATIONS

This protocol defines a protocol deviation as any noncompliance with the clinical trial protocol or Manual of Procedures (MOP) requirements. The noncompliance may be either on the part of the participant, the investigator, or the study site staff. As a result of deviations, corrective actions will be developed by the site and implemented promptly.

It will be the responsibility of the site investigator to use continuous vigilance to identify and report deviations within 7 working days of identification of the protocol deviation, or within 7 working days of the scheduled protocol-required activity. All deviations will be recorded in study source documents. Protocol deviations which are more substantial in nature will be sent to the reviewing Institutional Review Board (IRB) per their policies. The site investigator and PI will be responsible for knowing and adhering to the reviewing IRB requirements.

10.1.11 PUBLICATION AND DATA SHARING POLICY

This study will comply with the NIH Data Sharing Policy and Policy on the Dissemination of NIH-Funded Clinical Trial Information and the Clinical Trials Registration and Results Information Submission rule. As such, the full RCT will be registered at ClinicalTrials.gov, and results information from this trial will be submitted to ClinicalTrials.gov. In addition, every attempt will be made to publish results in peer-reviewed journals. We will submit final peer-reviewed journal manuscripts that arise from NIH funds to the digital archive PubMed Central upon acceptance for publication.

Further, we recognize that the dissemination of the research results plays an important role in the advancement of knowledge and research in the field, and are therefore committed to sharing the final research data and analytical codes used to process and analyze the data. We are also aware that the rights and privacy of people who participate in the research must be protected at all times.

All final data and code will be posted to institutional website(s) by the end of the project. We will post relevant data and code with corresponding working papers as they are released. The project will ensure any datasets resulting from the research and made publicly available will be free of identifiers that would permit linkages to individual research participants and variables that could lead to deductive disclosure of individual subjects.

We will publish the results of our work. Papers will primarily be published in peer-reviewed journals. Relevant data and code will also be posted to the website of any journal that publishes any papers resulting from this project, provided that the journal's website allows for this.

Our findings will also be disseminated via direct contact with government bodies and NGOs, as well as the media and presentations at policy and academic conferences. These outreach efforts will be made with the support of our local partner, IPA, which maintains strong relationships with policymakers and stakeholders at the local and national levels in Ghana. [name] will also use her extensive contacts in India, including previous collaborations with state governments and

the policy arms of her lab's partners, to disseminate the results in India as well – a hugely populous country with many similar small-holder farmers facing similar income instability concerns. Finally, we will use Cornell's expertise to disseminate the research results in a wide range of formats useful to broad audiences including blog posts, policy statements, and news articles.

